3. WORK PROPOSED

Overview: The study design for the present proposal is illustrated below. To obtain adequate power to detect a difference in prostate tumor apoptosis between the groups, the trial will require 30 patients per group. Based on our prior experience with the weight loss intervention we will be using in this trial, we are assuming a 15% dropout rate in the Weight Loss Group. Therefore, we are adding an additional 5 subjects to the Weight Loss Group to bring the total in this group to 35 and the total in the overall trial to 65.

Screening and Recruitment of Subjects - Minority Participation: Subjects will be recruited for the present trial from the VA Medical Center, Greater Los Angeles Health Care System. [name] conducts the urologic oncology clinic at the VA in which 130 new prostate cancer cases are diagnosed per year. Subjects with a new diagnosis of prostate cancer at the VA are offered standard therapies as well as the opportunity to participate in clinical trials. Subjects expressing interest in the weight loss trial will be given the consent form to review and the phone number of [name] research coordinator. Given the high prevalence of overweight and obese subjects (up to 70 % at our VA¹⁰), and given the high number of radical prostatectomy procedures performed at our VA (40/year), we anticipate no problem meeting our

recruitment goal of 65 subjects over 5-years. As well, given that 40-50% of men that undergo radical prostatectomy at the VA are AAM, we anticipate 40-50% of men in our clinical trials will be AAM.⁶² This is extremely important given the increased risk of obesity in AAM and the undue burden of increased morbidity and mortality of prostate cancer in AAM. For men randomized to the weight loss intervention group, the 4-9 week delay in radical prostatectomy has been shown not to increase the risk of biochemical recurrence.⁶³ However, we will not enter patients in this trial with a high risk of having advanced disease (Gleason Grade > 4+4) to avoid the potential risk (albeit extremely low) for progression during the weight loss intervention.

Inclusion Criteria:

1. Subject is overweight or obese (BMI > 25 kg/m²)
2. Patient with pathologically confirmed adenocarcinoma of the prostate and has elected to undergo radical prostatectomy
3. Able to adhere to physical activity intervention (able to walk for 10 minutes without rest)

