Study Procedures: Subjects will have their first study visit at the VA Greater Los Angeles Healthcare System Clinical Research Center (CRC) which will include subject consent and review of the entry criteria. Once consent is obtained, a medical history and physical exam will be performed including height, weight, and measurement of waist to hip ratio (anthropometrics). The urologist's DRE and clinical stage will be recorded from the subject's urology note, and prostate needle biopsy pathology including Gleason grade and percent of cores with cancer will be recorded. A fasting serum specimen will be collected for biomarker studies. A DEXA scan will be performed (to determine lean body mass to calculate caloric intake for the weight loss program) and to determine percent body fat. The Subject will then return home and during the next week will keep a 3-Day Food Diary (Appendix 2). Subject's will be randomized within 3-days of their initial visit and contacted at home with the results of the randomization.

Randomization: If a subject meets all eligibility criteria, the following steps will occur:

1. The study coordinator will FAX the subject's initials, study ID, and date of visit to the junior statistician (to be named).
2. Within 24 hours the statistician will inform the research coordinator of the randomization result (weight loss vs. No Weight Loss Group) and date of randomization. The research coordinator will inform the study subject of the results and schedule subsequent study visits.
3. The randomization will use a permuted block design with 5 blocks of size 13 (7 weight-loss and 6 no weight-loss).

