is significant after controlling for Gleason grade, stage and any demographic factors that are significantly different between the groups.

Secondary Outcome Variables: The secondary outcome variables are: the proliferative index in prostate cancer epithelium obtained from the radical prostatectomy specimen, the change in apoptotic and proliferative indices of malignant epithelium between the diagnostic prostate needle biopsy and corresponding radical prostatectomy, the change (baseline vs post-intervention) in serum IGF-related analytes: IGF-1 and IGFBP-1, the ex-vivo mitogenic and apoptotic activity of patient sera on LNCaP cells, and the change in body weight and percent body fat by DEXA over 4-9-weeks.

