Secondary Statistical Analyses: The statistical methods for these analyses will be analysis of variance (ANOVA), linear regression, and correlation analysis. ANOVA will be used to determine if the serum biomarkers (IGF-I, IGFBP-1, proliferation and apoptosis bioassays) change over the course of time. These models will include a term for time, treatment (weight-loss versus no weight loss) and the time by treatment interaction effect. We will also construct ANOVA models for weight and body fat over time to determine if the treatment by time effect (intervention effect) is significant. Next, linear regression models will be constructed for each biomarker to assess the factors that predict change in that marker. Predictors will include actual weight loss (percent change), group, grade, PSA, percent body fat, and demographic factors. These models will allow us to assess the direct effect of weight loss on each of the serum biomarkers and allow for the assessment of whether weight change or intervention is the primary factor predicting change in the biomarkers. This assessment is required due to the fact that the intervention will have varying effects on weight based on the amount of subject compliance with the weight loss regime. Regression models will also be constructed to compare the groups with respect to the pre-prostatectomy biomarkers and the tissue markers and the between group tissue markers (apoptosis, Ki67 staining). A separate model will be constructed for each marker including the predictors of group, grade, PSA, percent body fat and demographic factors. Next, we will construct regression models to determine if the biomarkers, or change in biomarkers, affect the post-op pathology. Ordinal regression will be used for post-op pathology. These models will include terms for the demographic factors and for each of the biomarkers. Since there are a large number of biomarkers we will first construct single biomarker models which will include the covariates for each outcome and then combine together all significant markers into multiple regression models. Finally, we will use the Spearman correlation to test for correlations between pre-prostatectomy biomarkers and the tissue markers. This analysis will specifically address **Objective 3** of the proposal, that being to determine if a correlation exists between serum biomarkers and tissue biomarkers. The Spearman correlation is a non-parametric rank based correlation measure that does not depend on the assumption that the markers are normally distributed.

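### The post-op pathology models leave out baseline disease severity, so any link between serum markers and pathology may be confounded and should not be read as an effect

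*Combined protocol and SAP*

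**What the plan says.** Everything cited is in the combined protocol and SAP, mostly in Section 3.

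- **Question.** Secondary Statistical Analyses states: "Next, we will construct regression models to determine if the biomarkers, or change in biomarkers, affect the post-op pathology". The model type follows: "Ordinal regression will be used for post-op pathology".
- **Terms.** "These models will include terms for the demographic factors and for each of the biomarkers". Because there are many markers, the plan then says "we will first construct single biomarker models which will include the covariates for each outcome", and markers significant at that step go together into a multiple regression. The covariates for the pathology outcome are not defined further.
- **Neighbouring models.** For the tissue markers: "A separate model will be constructed for each marker including the predictors of group, grade, PSA, percent body fat and demographic factors". The models for change in a serum marker also name group, grade, PSA and percent body fat. The adjusted primary model tests whether the treatment effect "is significant after controlling for Gleason grade, stage and any demographic factors that are significantly different between the groups".
- **Data available.** Study Procedures has the urologist's clinical stage taken from the clinic note, and "prostate needle biopsy pathology including Gleason grade and percent of cores with cancer will be recorded". Serum and Plasma Studies has PSA measured at baseline.
- **The waiting period.** Screening and Recruitment excludes men at high risk of advanced disease "to avoid the potential risk (albeit extremely low) for progression during the weight loss intervention".

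**The concern.** The verb *affect* puts a causal question to a model that has no term for how bad the cancer was at entry. Grade and extent at surgery depend heavily on grade and extent at diagnosis, so baseline severity is the obvious common cause to control. Of the regressions in the plan, this is the one whose outcome is closest to baseline severity, yet no severity measure is named for it.

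Randomization does not help. It balances the arms, but the exposure here is a man's serum level or his own change, and treatment group is not a named term either. The background section supplies a plausible non-causal route: it reports that obese men tend to have higher-grade disease, and that obesity lowers IGFBP-1. A marker could therefore track pathology through characteristics already present at baseline.

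What is at stake is the interpretation of one set of secondary models. A marker that only reflects disease at entry could be reported as influencing surgical pathology. A false positive at the single-marker step would pass into the combined model, which still has no severity term.

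**Working it through.** **1. The plan's own figure.** The only power statement is for the primary outcome: 30 men per arm, effect size 0.74, two-sided 0.05, 80% power. The exact noncentral t gives 80.5%, so it reproduces. It does not bear on the pathology models, for which no power is stated. It does supply n = 60.

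**2. Covariates side by side.**

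| Model | Severity terms named | Group named |
|---|---|---|
| Primary outcome, adjusted | Gleason grade, stage | yes (the tested effect) |
| Change in serum marker | grade, PSA | yes |
| Tissue markers | grade, PSA | yes |
| Post-op pathology | none | no |

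**3. Illustration of size.** Let *a* be the marker-severity correlation and *b* the severity-pathology correlation. Neither is in the documents; both are assumed. If the marker has no effect given severity, the two are still correlated at r = a × b. By the Fisher approximation, the test statistic is centred at atanh(r) × √(60 − 3):

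- a = 0, any b: r = 0, rejection 5%.
- a = 0.1, b = 0.5: r = 0.05, centre 0.38, rejection 6.7%.
- a = 0.1, b = 0.7: r = 0.07, centre 0.53, rejection 8.3%.
- a = 0.2, b = 0.5: r = 0.10, centre 0.76, rejection 11.8%.
- a = 0.4, b = 0.7: r = 0.28, centre 2.17, rejection 58%.

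This treats pathology as continuous. Grouping it into levels loses some information, so simulation gives somewhat lower values at the top. A Spearman test with four pathology levels gave 11% to 50% over a = 0.2 to 0.4 and b = 0.5 to 0.7. A three-level ordinal logit, the model type the plan names, gave the following (likelihood-ratio test at 5%, demographics in both models, 400 runs per cell):

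| a | b = 0.5: without / with severity | b = 0.7: without / with severity |
|---|---|---|
| 0 | 4.5% / 6.5% | 6.8% / 8.5% |
| 0.2 | 13.0% / 5.0% | 19.5% / 5.0% |
| 0.3 | 21.2% / 5.2% | 34.5% / 7.5% |
| 0.4 | 27.8% / 5.2% | 52.5% / 6.2% |

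Simulation error near 5% is √(0.05 × 0.95 / 400), about 1.1 points. Over the two methods the unadjusted range is about 11% to 53%.

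**4. Imperfect adjustment.** The adjusted columns assume that true severity is known. Biopsy grade and clinical stage are proxies. With proxy reliability R, the partial correlation left after adjustment is ab(1 − R) / √[(1 − a²R)(1 − b²R)], tested with √(60 − 4). At a = 0.3, b = 0.6:

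- R = 0.7: 0.054 / √(0.937 × 0.748) = 0.065, rejection 7.7%.
- R = 0.5: 0.090 / √(0.955 × 0.820) = 0.102, rejection 11.9%.
- Unadjusted: r = 0.18, centre 1.37, rejection 28%.

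Simulation over the whole grid with R = 0.5 to 0.7 (assumed) gave 5% to 22%. Adjustment removes much of the inflation, but not always all of it.

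**5. Change scores.** If a share *v* of the variance of a change is due to the randomized arm, which is unrelated to severity in expectation, the correlation of the change with severity is the within-arm correlation times √(1 − v). With v = 0.5 (assumed), 0.30 falls to 0.30 × 0.707 = 0.21. Levels have no such protection at baseline.

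**The case against.** Several points on the other side stand.

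- *The plan may already intend adjustment.* The reference to covariates for each outcome is undefined, and a reader could take grade and PSA as implied by the sentences before it. PSA could also be counted as a serum biomarker. But the only covariates stated for pathology are demographic, the section's own list of serum biomarkers leaves PSA out, and flow-chart footnote 1 lists PSA as an additional study. Grade and stage have no such reading. The subgroup analyses by PSA, stage and Gleason score are not adjustment.
- *Confounding is not demonstrated.* Correct. The inflation is driven by an assumed correlation and nearly vanishes at 0 to 0.1. *May be confounded* is as far as the documents go.
- *The analysis is peripheral.* Also correct. Post-op pathology is not defined and is not among the listed secondary outcomes.

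A reader might infer three stronger things. One is that surgical pathology was already fixed at randomization. The remark on low risk concerns progression during the wait; it fits that view but does not establish it. A second is that every association found will be spurious, which needs correlations that the plan does not give. The third is that these models pick the markers for the next trial. They do not: Objective 3 rests surrogate choice on serum-tissue marker correlations, and the plan assigns that objective to the Spearman analysis.

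**Conclusion.** The concern holds as a defect of model specification and wording in a secondary, effectively exploratory analysis. As written, the post-op pathology models name no measure of baseline severity, although biopsy Gleason grade, clinical stage and PSA are in hand. Their results cannot support the statement that a marker, or its change, affects pathology.

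The size is conditional. For a null marker at n = 60, roughly 11% to 53% false positives follow if the marker-severity correlation is 0.2 to 0.4 and the severity-pathology correlation is 0.5 to 0.7; there is little inflation at 0 to 0.1. Change scores are probably less exposed than levels. The primary comparison of apoptotic index, the listed secondary outcomes and Objective 3 do not depend on these models. The change is worth making because it is cheap and removes a foreseeable misreading.

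**What to change.** In Secondary Statistical Analyses:

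1. Add baseline severity to every post-op pathology model, single-marker and combined: biopsy Gleason grade, clinical stage and baseline PSA, preferably as one combined risk term defined before the data are examined.
2. Add treatment group to the same models. Group should not be added alone: it removes the arm-driven part of a marker change, which is the part unrelated to baseline severity, and leaves the part that may be confounded.
3. Replace *affect* with *are associated with*, and label the models exploratory.
4. State that no effect of the intervention on pathology will be inferred from them.

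The cost is wording plus a few degrees of freedom. A combined term and group use two parameters per model; separate terms use at least four (grade, stage, PSA, group), more if grade or stage is entered as categories. With about 60 men and an ordinal outcome, that favours the combined term. No new data are needed. Because the severity measures are proxies, some confounding may remain, which is a further reason for the associational wording.

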Objective 3. To determine if the weight loss-induced changes in the serum biomarkers/bioassays from Objective 2 correlate with prostate tissue histo-marker changes in Objective 1. This analysis will assess if these serum biomarkers can therefore be used as surrogate biomarkers for future large-scale secondary prevention trials in overweight and obese prostate cancer survivors to monitor the success of weight loss intervention. For example, if the degree of LNCaP apoptosis in the ex-vivo apoptosis bioassay correlates with apoptosis in prostate cancer tissue, then the ex-vivo apoptosis bioassay may serve as a useful intermediate bioassay in large-scale trials to monitor the potential efficacy of weight loss in delaying prostate cancer progression or similarly, IGF-I or IGFBP-1 may prove to be the most predictive circulating indicator of prostate tumor apoptosis.

Long-Term Objectives: Our long term objective is to establish weight loss as an effective treatment to slow prostate cancer progression (secondary prevention) in overweight and obese prostate cancer survivors. If our presently proposed trial is found to be positive, indicating that weight loss results in improvements in the proliferative and apoptotic indices in malignant epithelium, our next trial (**intermediate goal**) will be a large scale, multi-site study evaluating if weight loss impacts on PSA doubling time in men with a rising PSA after primary therapy for prostate cancer. Given that PSA doubling time is becoming established as a surrogate for prostate cancer survival, results from this larger scale trial will determine the need for weight loss strategies in overweight and obese prostate cancer survivors.

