Radical Prostatectomy–Tissue Collection: At the time of prostatectomy, frozen tissue blocks of benign prostate tissue and prostate carcinoma will be obtained immediately following surgery. Frozen sections will be evaluated by a pathologist to ensure the quality of the specimens and verify if the specimen represents benign or malignant tissue. Fresh tissue will be embedded in OCT (polyvinyl alcohol and polyethylene glycol), 'snap frozen', and stored at -80°. The remainder of the tissue will be fixed in 10% neutral buffered formalin and embedded in paraffin for routine histology and immunohistochemistry studies. The amount of fresh tissue obtained will vary depending on the size of the carcinoma, but our experience has shown that at least one 1.0 x 0.5 x 1.0 cm tissue block representative of the carcinoma, and a similar sized block of benign prostate tissue can be retrieved from most prostatectomy specimens. At the time of radical prostatectomy a sample of fat from the anterior surface of the prostate, a sample of subcutaneous fat and fat from the inner abdominal wall will be collected. Half of the tissue will be flash frozen and used for genomic and proteomic analysis. The other half will be cultured at 37 degrees centigrade in M199 media and the conditioned media will be harvested and used to quantify secreted inflammatory cytokines such as IL8 and IL6.

Serum and Plasma Studies-Overview: Serum insulin, Free and Total Testosterone, Estradiol, Leptin, IGF-1, IGFBP-1, PSA, lipids, ex-vivo mitogenic bioassay, and the ex-vivo apoptosis assay will be performed at baseline and prior to radical prostatectomy in all subject in the Weight Loss Group and control group. We are measuring PSA levels given that PSA represents an established tumor marker of disease progression in prostate cancer and weight loss may potentially decrease the PSA. PSA levels will also be measured in subjects in the control and Weight Loss Groups post-operatively every 6-months (for the 10-year study duration) as is routine in our GU Oncology clinic at the VA. White blood cells will be collected from the buffy

coat, RNA extracted, and PCR arrays will be performed to quantitate inflammatory cytokines and chemokines. Subject weights will also be recorded at these visits.

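### In the post-operative pathology models, biomarkers are screened by significance and refitted on the same roughly 60 men with no safeguard, so final-model p-values and coefficients favour whatever was selected

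*Combined protocol and SAP*

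**What the plan says.** The rule is in section 3, Statistical Analysis, under Secondary Statistical Analyses. The plan will build "regression models to determine if the biomarkers, or change in biomarkers, affect the post-op pathology", using ordinal regression with demographic terms. It sets out two steps. The first is a separate model for every marker, with covariates, which the plan justifies by how many biomarkers there are. The second step, for whichever markers pass the first, is to "then combine together all significant markers into multiple regression models".

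The plan gives no significance level for the screen, multiplicity correction, limit on candidates, shrinkage, internal validation or separate data set, and it does not call these models exploratory. The data are those of randomized men who complete the study, planned as at least 30 per group.

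The candidate list is not fixed. Earlier in the same paragraph the plan speaks of "serum biomarkers (IGF-I, IGFBP-1, proliferation and apoptosis bioassays", which is four. The Serum and Plasma Studies overview lists a wider set: "Serum insulin, Free and Total Testosterone, Estradiol, Leptin, IGF-1, IGFBP-1, PSA, lipids, ex-vivo mitogenic bioassay, and the ex-vivo apoptosis assay". That is 11 if lipids count as one, with PCR arrays in addition. Either the level or the change of a marker may be used.

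**The concern.** A marker reaches the combined model only because its p-value was small in these same men. Refitting it in those men is not an independent test. Its p-value no longer has its nominal meaning, and its coefficient is too large on average, because the markers whose estimates happened to be small were left out.

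The practical risk concerns what is carried forward. The protocol wants "surrogate biomarkers for future large-scale secondary prevention trials". A marker reported from this model as an independent predictor of pathology would look like support for that use, even if it entered by chance.

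**Working it through.** **Inputs.**
- Evaluable men: 60 (30 + 30), from Sample Size Determination. This is the planned minimum.
- Screening level: not stated. I assume 0.05 two-sided, which the plan states only for the primary comparison.
- Candidates k: 4 (markers named in the analysis paragraph), 8 (the same four as level and as change), 11 (serum overview) or 22 (those 11 as level and as change).
- Correlation between markers: not stated. I take 0, 0.3 and 0.5.
- Covariates: number not stated. I take five in the simulation.

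**1. The plan's own figure.** The 60 men come from the primary t-test. With 30 per group and effect size 0.74, the normal approximation gives Φ(0.74 × √(30/2) − 1.960) = Φ(0.906) = 81.8%, and the noncentral t gives 80.5%. The stated 80% is reproduced. The plan gives no error rate for the biomarker screen.

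**2. Chance that at least one null marker passes the screen.** For independent markers this is 1 − 0.95^k:
- k = 4: 1 − 0.95^4 = 18.5%
- k = 8: 33.7%
- k = 11: 43.1%
- k = 14: 51.2% (the first k above one half)
- k = 22: 67.6%, with 22 × 0.05 = 1.1 false entries expected

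With a screen at 0.10 instead, k = 4, 8 and 22 give 34%, 57% and 90%.

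**3. Chance that a null marker is still significant after the refit.** I simulated the two steps with n = 60, five covariates and all markers null, using a linear model as a stand-in for ordinal regression. Several thousand data sets were run per setting, and separate runs agree to within about two percentage points.

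| Candidates | Independent | Correlation 0.3 | Correlation 0.5 |
|---|---|---|---|
| 4 | 18% | 15% | 12% |
| 8 | 33% | 25% | 18% |
| 11 | 42% | 29% | 20% |
| 22 | 65% | 40% | 25% |

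With independent markers, 77% to 96% of the false markers that passed the screen stayed below 0.05 in the refit, so the second step removes few of them. With correlated markers it removes more. At k = 22 and correlation 0.3, some false marker enters in 57% of trials and remains significant in about 40%.

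**4. Size of the overstatement.** Without covariates, passing at 0.05 in 60 men needs |r| ≥ 2.00/√(2.00² + 58) = 0.25. Null markers that pass therefore show a mean absolute correlation of about 0.30 with the outcome, when the truth is zero.

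**5. Check on the replacement test.** A joint 4-df likelihood ratio test referred to chi-square (critical value 9.488) is itself too liberal at this size. In a linear model with c covariates the residual df are d = 60 − 1 − c − 4, and LR = 60 × ln(1 + 4F/d). Rejection then means F > (e^(9.488/60) − 1) × d/4.
- c = 5, d = 50: F > 2.14, which has null probability 8.9%.
- c = 8, d = 47: F > 2.01, which has null probability 10.8%.

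An ordinal model gives about 9%. A small-sample reference is therefore needed.

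**The case against.** Four points can be made for the plan.

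**The analysis is peripheral.** Post-operative pathology is not among the listed secondary outcome variables, and the primary comparison does not depend on it. This stands, and it limits the weight of the point.

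**It is not the analysis for Objective 3.** A reader might infer that this rule chooses the surrogate markers. The documents do not support that. The plan assigns Objective 3 to Spearman correlations between serum and tissue markers, where nothing enters by p-value. The link to later trials is indirect, through how a reported predictor of pathology would be read.

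**The error rate may be modest.** A reader might also infer that the final model will usually contain a false predictor. That needs many weakly correlated candidates. On the narrow count of four markers the rate is about 18%, and with level and change about 33% if independent. Level and change come from the same measurements, and IGF-axis markers are related, so independence is the least plausible case. At correlation 0.5 even 22 candidates give about 25%. The flow-chart footnote also calls insulin, PSA and lipids additional studies. Against this, the screening sentence itself justifies the procedure by the large number of biomarkers, and the plan sets no limit.

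**The simulation uses a linear model.** The plan specifies ordinal regression, so the simulated percentages are approximate. The closed-form entry rates assume only independent tests that hold 0.05.

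**Conclusion.** The concern holds for the post-operative pathology models. The plan prescribes selection by significance and a refit in the same men, and offers nothing to offset the resulting bias. In every setting tabulated the chance of a falsely significant marker in the final model exceeds 5%: from about 12% (4 candidates, correlation 0.5) to about 65% (22 independent candidates).

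These figures assume a 0.05 screen, 60 men and no true association for any candidate. The documents support neither a claim that false predictors will usually appear nor a claim that Objective 3 is compromised. This is a low-severity point about a secondary analysis, worth correcting because the correction is cheap.

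**What to change.** For the post-operative pathology outcome, replace screen-and-refit with one pre-specified ordinal model:
- Enter the four Objective 2 markers (IGF-1, IGFBP-1, ex-vivo proliferation and ex-vivo apoptosis) together with the named covariates, with no entry by p-value.
- Declare in advance one form for each marker, level or change, so that there are exactly four marker terms.
- Test the four jointly at 0.05 before reading single markers. Use a permutation or parametric-bootstrap likelihood ratio test, or an F test if the model is linear, and not the plain chi-square reference.
- Report all other markers one at a time with confidence intervals, labelled exploratory.

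The joint test protects against the case where none of the four matters. It does not fully control error for single markers once one is real, so individual results should still be read with their intervals.

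The cost is SAP wording, with no new data, visits or patients. The downside is that the remaining serum markers no longer enter a combined model.
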